 - A serum pregnancy test is needed on Day 1 only if the urine pregnancy test is positive (see Section 4.1.1 for definition of “childbearing potential”).
- History of alcohol, drug (e.g., tetrahydrocannabinol [THC], marijuana), or chemical abuse within the 12 months prior to screening as determined by the investigator
- Need for systemic anti-coagulation with warfarin, other oral or injectable anti-coagulants, or anti-platelet agents other than NSAIDs, aspirin, and other salicylates
- History of non-gallstone-related pancreatitis or chronic pancreatitis
- History of hospitalizations or transfusion for a GI bleed
- History of cerebrovascular accident (CVA) within 10 years or any history of hemorrhagic CVA
- History of spontaneous intracranial hemorrhage or history of traumatic intracranial hemorrhage within 10 years
- Known bleeding diathesis
- Screening 12-lead ECG that demonstrates clinically relevant abnormalities that may affect patient safety or interpretation of study results, including
 - QT interval corrected using Fridericia’s formula (QTcF) > 440 ms demonstrated by at least two ECGs > 30 minutes apart
- History of ventricular dysrhythmias or risk factors for ventricular dysrhythmias such as long QT syndrome and other genetic risk factors (e.g., Brugada syndrome), structural heart disease (e.g., severe left ventricular systolic dysfunction, severe left ventricular hypertrophy), coronary heart disease (symptomatic or with ischemia demonstrated by diagnostic testing, prior coronary artery bypass grafting, or coronary lesions > 70% diameter stenosis that have not been or cannot be re-vascularized), clinically significant electrolyte abnormalities (e.g., hypokalemia, hypomagnesemia, hypocalcemia), or family history of sudden unexplained death or cardiac ion channel mutations (e.g., congenital long QT syndrome)

- Current treatment with medications that are well known to prolong the QT interval (see <https://crediblemeds.org/index.php/login/dlcheck>) at doses that have a clinically meaningful effect on QT, as determined by the investigator; the investigator may contact the Sponsor for confirmation if needed
- Current treatment with astemizole, terfenadine, and/or ebastine
- Any condition possibly affecting oral drug absorption (e.g., gastrectomy, clinically significant diabetic gastroenteropathy, or certain types of bariatric surgery such as gastric bypass)

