4.4.2 Cautionary Therapy

4.4.2.1 Acid-Reducing Agents

Patients who use antacids (e.g., Pepto-Bismol[®], Rolaid[®]) for symptomatic relief of heartburn should take fenebrutinib or matching placebo at least 2 hours before or 2 hours after antacid administration because gastric acid improves fenebrutinib absorption.

Patients may be treated with PPIs or H2RAs at up to the maximum recommended dose according to local labeling. The dose should remain stable for at least the 2 weeks before randomization and throughout the study.

At visits with scheduled PK assessments (see [Appendix 1](#)), any use of PPIs, H2RAs, and/or other antacids (e.g., Pepto-Bismol[®], Roloids[®]) should be recorded as concomitant medications, including the date and time of last administration.

4.4.2.2 *Statins*

Several lipid-lowering agents (statins) are metabolized by CYP3A (simvastatin, lovastatin) and/or transported by BCRP (rosuvastatin, atorvastatin), and thus may be affected by drug-drug interaction with fenebrutinib, therefore, dose adjustments of these medications should be considered (Kellick et al. 2014).

- *Simvastatin: recommended maximum dose of 10 mg/day*
- *Lovastatin: recommended maximum dose of 20 mg/day*
- *Rosuvastatin: recommended maximum dose of 10 mg/day*
- *Atorvastatin: recommended maximum dose of 20 mg/day*

The use of statins has been associated with myopathy, which can manifest as weakness, tenderness or muscle pain with elevations of creatine kinase (CK) above ten times the ULN. In severe cases, myopathy can cause rhabdomyolysis with or without acute kidney injury secondary to myoglobinuria, and rare fatalities due to rhabdomyolysis have occurred. The risk of myopathy is increased by elevated plasma levels of statins. Predisposing factors for myopathy include advanced age (≥ 65 years), female gender, uncontrolled hypothyroidism, renal impairment, or the use of concomitant medications that increase the plasma levels of the statin.

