4.5.7 Laboratory, [REDACTED] and Other Biological Samples

Samples for the following laboratory tests will be sent to one or several central laboratories for analysis as per the Schedule of Activities in [Appendix 1](#). Laboratory tests prior to randomization and dosing may be performed locally on Day 0, if central laboratory tests are not available due to sampling handling problems, breakage, or lab error.

- Hematology: hemoglobin, hematocrit, platelet count, RBC count, WBC count, percent and absolute differential counts (neutrophils, bands, lymphocytes, monocytes, eosinophils, basophils, other cells)
- Serum chemistry: sodium, potassium, chloride, bicarbonate, glucose, BUN, creatinine, calcium, phosphorus, magnesium, total and direct bilirubin, total protein, albumin, ALT, AST, LDH, alkaline phosphatase, creatine phosphokinase, CRP, lipase, and uric acid
- Urinalysis including dipstick (pH, specific gravity, glucose, protein, ketones, blood) and microscopic examination (sediment, RBCs, WBCs, casts, crystals, epithelial cells, bacteria)
- Coagulation: INR, activated PTT, PT, fibrinogen
- Fasting lipid panel
- Viral serology
- Hepatitis B: HBsAg, total HBcAb, and hepatitis B surface antibody
- Hepatitis C antibody

█ [REDACTED]

█ [REDACTED]

- The following samples will be sent to the Sponsor or a designee for analysis:

█ [REDACTED]

- Plasma samples for PK analysis
- See the Schedule of Activities provided in [Appendix 1](#) for specific timepoints.
- Samples for the following laboratory tests will be sent to the study site's local laboratory for analysis:
- Pregnancy test

All women of childbearing potential (including those who have had a tubal ligation) will have a serum pregnancy test at screening. Urine pregnancy tests will be performed at specified subsequent visits. If a urine pregnancy test result is positive, it must be confirmed by a serum pregnancy test. Should a positive result be recorded at any time, the procedures detailed in Section [5.4.3](#) should be followed. If a local urine pregnancy test shows a positive result, then study drug will not be administered that day. Other study procedures should also be postponed and the result must be confirmed by a serum pregnancy test prior to proceeding.

- QFT or PPD (if QFT not available) and additional procedures (e.g., chest X-ray) to rule out latent or active TB per local guidelines

See the Schedule of Activities provided in [Appendix 1](#) for specific timepoints.

[REDACTED]

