| Fenebrutinib/placebo administration in clinic ^{q, r} | | | x | x | x | x | | | | | |
| Drug Dispensing | | | x | | | x | | | | | |
| Hematology ^s | x | x | x | x | x | x | | x | x | x | x ^k |
| Chemistry ^t | x | x | x | x | x | x | | x | x | x | x ^k |
| Fasting Lipid Panel | | | x | | | x | | x | x | | |
| Coagulation studies ^u | x | | | | | | | | | x | x ^k |
| Pregnancy test ^v | x | | x | x | x | x | | x | x | x | |
| Urinalysis ^w | x | | x | | | | | x | x | x | |
| | | | | | | | | | | | |
| FricTest (for patients with dermographism only) | x | | x | | | | | x | x | x | |
| Plasma PK assessment ^y | | | x | x | | | | x | | x | x ^k |
| | | | | | | | | | | | |
| Phone call ^{bb} | | | | | | | x | | | | |

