- ^q On mandatory morning clinic visit days *during the treatment period* (Days 1, 8, 29, and 57), patients should be instructed that the morning dose of study drug will be taken in the clinic. On other clinic visit days, if the visit occurs in the morning, the patient should be instructed that the morning dose of study drug will be taken in the clinic. The morning dose should be taken after all pre-dose assessments are complete (i.e., ECG, questionnaires, and PK and ██████████ sample collection).
- ^e Patients will take fenebrutinib/placebo BID approximately every 12 hours starting on Day 1 and ending on Day 56 (pm) or the day before (pm) the Day 57 visit if it does not occur on Day 57. One dose (a total of 4 tablets) of fenebrutinib/placebo should be taken with water by mouth BID (a total of 8 tablets each day). The dates and times of the most recent prior meal, last dose of oral study drug (prior to clinic visit), and timing of study drug administration in clinic should be recorded at each clinic visit.
- ^s Includes WBC count, RBC count, hemoglobin, hematocrit, platelet count, and WBC differential (i.e., neutrophils, eosinophils, basophils, monocytes, lymphocytes, and other cells if present).
- ^t Includes sodium, potassium, chloride, bicarbonate, glucose, BUN or urea, creatinine, total protein, albumin, phosphorus, calcium, total and direct bilirubin, alkaline phosphatase, ALT, AST, uric acid, LDH, CRP, and lipase.
- ^u Includes PT, PTT, INR, and fibrinogen.
- ^v All women of childbearing potential, including those who have had a tubal ligation, will have a serum pregnancy test at screening. Urine pregnancy tests will be performed locally at specified subsequent visits. If a urine pregnancy test result is positive, it must be confirmed by a serum pregnancy test (performed locally).
- ^w Includes dipstick, including pH, specific gravity, glucose, protein, ketones, blood, and microscopic examination (e.g., sediment, RBCs, WBCs, casts, crystals, epithelial cells, bacteria if present).

Appendix 1
Schedule of Activities (Cohorts 1 and 2) (cont.)

■ [REDACTED]

y Collect PK samples prior to drug administration, and the patient should be fasting overnight for > 8 hours.

■ [REDACTED]

■ [REDACTED]

^{bb} Site staff to remind patients to take the study drug and to complete their eDiaries.

Appendix 2

Childbearing Potential, Pregnancy Testing, and Contraception

For Women

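### Section 4.5.7 puts magnesium and creatine phosphokinase in the chemistry panel; Appendix 1 footnote t lists the same panel without them, and the two must be reconciled

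*Combined protocol and SAP*

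**What the plan says.** **Chemistry content.** Section 4.5.7 introduces its central-laboratory tests with "Samples for the following laboratory tests will be sent to one or several central laboratories for analysis as per the Schedule of Activities". Its serum chemistry entry includes "calcium, phosphorus, magnesium, total and direct bilirubin, total protein, albumin, ALT, AST, LDH, alkaline phosphatase, creatine phosphokinase, CRP, lipase, and uric acid".

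**Chemistry schedule.** Appendix 1 has a chemistry row, and footnote t defines that row. The later part of the footnote reads "phosphorus, calcium, total and direct bilirubin, alkaline phosphatase, ALT, AST, uric acid, LDH, CRP, and lipase". The earlier part covers the common electrolytes, glucose, renal markers and proteins. Magnesium and CPK are in neither part.

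**Where the two analytes matter.** Section 4.4.2.2 allows statins with caution, says that fenebrutinib may interact with several of them, and describes myopathy as weakness, tenderness or "muscle pain with elevations of creatine kinase (CK) above ten times the ULN". Section 4.1.2 includes, among the risk factors for ventricular dysrhythmia that exclude a patient, "clinically significant electrolyte abnormalities (e.g., hypokalemia, hypomagnesemia, hypocalcemia". Sections 4.5.8 and 5.1.1.7 ask the investigator to look for electrolyte abnormalities after a QTcF rise. Table 1 makes change from baseline in laboratory results a safety endpoint.

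**Coagulation.** The Appendix 1 row "Coagulation studies" is marked at Day -14, at early termination and, optionally, at unscheduled visits. Its footnote reads "Includes PT, PTT, INR, and fibrinogen".

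**The concern.** Two current passages define one blood sample differently, and no other passage resolves it. Whoever sets up the panel has to choose a page. A laboratory working from the schedule could leave out both analytes without knowing that it had departed from the protocol.

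No other scheduled analyte stands in for CPK as the marker by which the protocol describes statin myopathy. Magnesium is the only one of the three electrolytes in the exclusion example that footnote t lacks; potassium and calcium are both there. If the analytes are not run, there is no baseline value to set against a later abnormal result, and the laboratory safety endpoint has no data for either.

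**Working it through.** No power or sample-size figure is involved. The check compares the two lists and counts schedule marks.

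**1. List comparison.** Total and direct bilirubin count as two, and BUN in one list is matched to BUN or urea in the other.

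| Group | Section 4.5.7 | Footnote t |
|---|---|---|
| Potassium, sodium, bicarbonate, chloride, phosphorus, calcium | 6 | 6 |
| Creatinine, BUN, glucose, uric acid | 4 | 4 |
| AST, ALT, alkaline phosphatase, LDH, two bilirubins | 6 | 6 |
| Albumin, total protein | 2 | 2 |
| Lipase, CRP | 2 | 2 |
| Magnesium | 1 | 0 |
| CPK | 1 | 0 |
| **Total** | **22** | **20** |

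22 − 20 = 2. Nothing in footnote t is absent from Section 4.5.7.

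**2. Chemistry visits.** The row is marked at Days -14, -7, 1, 8, 15, 29, 57 and 85, which is 8 scheduled visits, plus early termination and optional unscheduled visits. Day 43 is a phone call and is blank. A patient who enters the open-label extension straight from Day 57 skips Day 85 and has 7. After the first dose and up to the end of treatment there are 4 (Days 8, 15, 29 and 57).

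**3. The two branches.**

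| If this governs | Magnesium and CPK measured at |
|---|---|
| Section 4.5.7 | 8 of 8 scheduled visits |
| Footnote t | 0 of 8 scheduled visits |

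In the second branch, 2 analytes × 4 visits = 8 treatment-period results per patient are lost, together with the baseline values.

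**4. Coagulation row.** There is a mark at Day -14, then eight blanks (Days -7, 1, 8, 15, 29, 43, 57 and 85), then early termination and optional unscheduled. The table was read from a PDF, but the column positions agree with the neighbouring rows, including the Day 43 phone call. A patient who completes the study therefore has 0 scheduled coagulation results after screening.

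**The case against.** The best defence is that Section 4.5.7 sets content and Appendix 1 sets timing. Later lines of Section 4.5.7 send the reader to the appendix for timepoints, and footnote t is worded as an inclusion that need not be exhaustive. Sampling procedures are left to a laboratory manual outside these documents, which may list all 22 analytes. This stands as far as it goes: it is not established that magnesium and CPK go unmeasured. It does not remove the conflict, because footnote t reads as a full panel and repeats every other analyte.

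It can also be said that the clinical links are loose. Section 4.4.2.2 sets no CK monitoring rule and asks that statin dose adjustment be considered. Hypomagnesemia is an example within a risk-factor criterion and is not one of the listed screening-laboratory thresholds. Electrolyte review after a QTcF rise is triggered by the event. Table 1 names no analytes. All of this is correct, and it limits the point to an inconsistency about which safety tests are run.

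A reader might infer that muscle, QT, bleeding and liver risks are not measured on drug. The documents do not support that. ALT, AST, bilirubin, albumin, potassium, calcium, hemoglobin and platelets are scheduled at Days 8, 15, 29 and 57. An ECG is scheduled at Day 8. Bleeding of at least moderate severity is an adverse event of special interest.

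A reader might also treat the blank coagulation row as an error. No passage promises coagulation tests on treatment. Section 5.1 describes routine laboratory safety as hematology, chemistry and urinalysis, Section 5.1.1.6 monitors the liver by AST/ALT and total bilirubin, and Section 5.1.1.3 describes a platelet-function mechanism that PT and PTT do not directly test. Adding a coagulation sample is a design preference.

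**Conclusion.** The inconsistency is real and confined to two analytes. Its consequence depends on which text the laboratory follows: magnesium and CPK at 8 of 8 scheduled chemistry visits under Section 4.5.7, or 0 of 8 under footnote t. The documents do not show which occurs. Panel content would be set without regard to arm, so the footnote t branch loses information and does not by itself bias the comparison with placebo.

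Coagulation is a secondary observation. Post-screening results can come only from early-termination and optional unscheduled visits. Patients reach those because of how they fared or whether they stayed, so the results should not support a between-arm comparison. It is tempting to put a number on this by applying the 10% dropout assumption to the roughly 120 patients of Cohort 2 (0.10 × 120 = 12). That does not hold. Sections 4.6.1 and 4.6.2 first ask patients who discontinue to attend the 4-week safety follow-up visit, which has no coagulation mark, and send those who refuse it to early termination. The documents give no basis for the split.

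**What to change.** Add magnesium and creatine phosphokinase to Appendix 1 footnote t so that it matches Section 4.5.7, and confirm that the laboratory manual carries the same 22 analytes. The cost is two assays on a sample already drawn and the review of a few incidental CK rises.

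Section 1.2.3 already counts 37 patients with CSU given fenebrutinib or placebo. It is worth asking which panel has been run so far and recording in the Data Analysis Plan for which patients the two analytes exist.

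For coagulation, state in the Data Analysis Plan that post-screening results will be listed and not compared between arms. This needs no new sample.

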Appendix 2 Childbearing Potential, Pregnancy Testing, and Contraception (cont.)

- Sole sexual partner consisting of surgically sterilized male partner with appropriate postsurgical verification of the absence of spermatozoa in the ejaculate. Patients may provide verbal confirmation that the partner completed appropriate follow-up after vasectomy. Sites are not required to obtain partner medical records.
- ¹ Women using estrogen-containing hormonal contraceptives as a method of contraception must also use a barrier such as a male condom in conjunction with the hormonal contraceptives.
- **For Men:**
 - All men must agree to remain abstinent (refrain from heterosexual intercourse) or use contraceptive measures, and agreement to refrain from donating sperm, as defined below:
 - With female partners of childbearing potential or pregnant female partners, men must remain abstinent or use a condom during the treatment period and for at least 4 weeks after the last dose of fenebrutinib to avoid exposing the embryo. Men must refrain from donating sperm during this same period.

For Men and Women

The reliability of sexual abstinence should be evaluated in relation to the duration of the clinical trial and the preferred and usual lifestyle of the patient. Periodic abstinence (e.g., calendar, ovulation, symptothermal, and post-ovulation methods) and withdrawal are not acceptable methods of contraception.

Appendix 3 Urticaria Patient Daily eDiary

General Instructions

Please answer each question to the best of your ability.

There are no right or wrong answers.

For each question, please choose the response that describes your experience.

Please pay close attention to the timeframe of interest. Some questions ask about the **past 12 hours**, while others ask about the **past 24 hours**.

Instructions for Counting the Number of Hives and Measuring the Size of the Largest Hive

Count each hive separately even if you have more than one hive grouped together with other hives.

Please use the ruler that you have been given to measure the size of your largest hive. If you need help, please have someone else take this measurement for you. **Please do not measure a group of hives as one hive.**

Appendix 3 Urticaria Patient Daily eDiary (cont.)

Today's Date

| | | | | | | | | | | |
|--|--|---|--|--|--|---|--|--|--|--|
| | | - | | | | - | | | | |
|--|--|---|--|--|--|---|--|--|--|--|

Day Month Year

Please complete this Section every morning throughout the duration of the study. (Please circle only one response.)

- Thinking about the **past 12 hours**, please record the severity of itch and the number of hives you may have had associated with your skin condition. **Please count each hive separately** even if you have more than one hive grouped together with other hives.

| Itch (severity) | Hives (number) |
|--|--|
| 0 = none 1 = mild 2 = moderate 3 = severe | 0 = none 1 = between 1 and 6 hives 2 = between 7 and 12 hives 3 = greater than 12 hives |

This next question asks you to estimate the size of your largest hive in centimeters (cm). Please use the ruler that you have been provided with to make this measurement. If your largest hive is located on your back or in a place that is hard to reach, please have someone else take this measurement for you. When measuring the largest hive size, **please do not measure a group of hives as one hive.**

| Largest Hive (size) |
|--|
| 0 = none 1 = less than 1.25 centimeter (cm) 2 = between 1.25 centimeter (cm) and 2.5 centimeters (cm) 3 = greater than 2.5 centimeters (cm) |

Appendix 3 Urticaria Patient Daily eDiary (cont.)

Today's Date

| | | | | | | | | | | |
|--|--|---|--|--|--|---|--|--|--|--|
| | | - | | | | - | | | | |
|--|--|---|--|--|--|---|--|--|--|--|

Day Month Year

Please complete this Section every evening throughout the duration of the study. (Please circle only one response.)

2. Thinking about the **past 12 hours**, please record the severity of itch and the number of hives you may have had associated with your skin condition. **Please count each hive separately** even if you have more one than one hive grouped together with other hives.

| Itch (severity) | Hives (number) |
|-----------------|----------------------------|
| 0 = none | 0 = none |
| 1 = mild | 1 = between 1 and 6 hives |
| 2 = moderate | 2 = between 7 and 12 hives |
| 3 = severe | 3 = greater than 12 hives |

This next question asks you to estimate the size of your largest hive in centimeters (cm). Please use the ruler that you have been provided with to make this measurement. If your largest hive is located on your back or in a place that is hard to reach, please have someone else take this measurement for you. When measuring the largest hive size, **please do not measure a group of hives as one hive.**

| Largest Hive (size) |
|---|
| 0 = none |
| 1 = less than 1.25 centimeter (cm) |
| 2 = between 1.25 centimeter (cm) and 2.5 centimeters (cm) |
| 3 = greater than 2.5 centimeters (cm) |

Appendix 3
Urticaria Patient Daily eDiary (cont.)

Today's Date

| | | | | | | | | | |
|-----|--|-------|--|--|--|------|--|--|--|
| | | - | | | | - | | | |
| Day | | Month | | | | Year | | | |

Please complete this Section twice each day (a.m. and p.m.) throughout the duration of the study (preferably at the same time each day).

(Please circle only one response.)

3. Please rate how much your hives or itch interfered with your sleep during the **past 24 hours**.

- 0 No interference
- 1 Mild, little interference with sleep
- 2 Moderate, awoke occasionally, some interference with sleep
- 3 Substantial, woke up often, severe interference with sleep

4. Please rate how much your hives or itch interfered with your daily activities during **the past 24 hours**. This could include work, school, sports, hobbies, and activities with friends and family.

- 0 No interference
- 1 Mild, little interference with daily activities
- 2 Moderate, some interference with daily activities
- 3 Substantial, severe interference with daily activities

